16.3.4.2 Assessment of the Effect of Evobrutinib on other ECG Parameters

The effect of evobrutinib and MSC2729909A plasma concentrations on baseline-corrected measurements of uncorrected QT intervals, PR and QRS intervals, and HR will be visually assessed by plots of the ECG measurements versus time-matched evobrutinib and MSC2729909A plasma concentrations with trend lines.

CCI

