5.3 Lifestyle Considerations

5.3.1 Meals and Dietary Restrictions

- Participants will abstain from consuming Seville oranges, grapefruit or grapefruit juice, pomelos, exotic citrus fruits, grapefruit hybrids, or fruit juices from these fruits from 14 days before the start of study intervention until after the final dose.
- Participants will receive standardized meals on Day -1 of each period at customary times.
- On Day 1 of each period the participants will be fasting (no food, no beverages, only water is allowed) from at least 10 hours before and until 4 hours after drug administration. Ingestion of water between 1 hour predose and until 1 hour postdose will not be allowed. 4 hours after drug

administration, a standardized lunch will be served. An afternoon snack will be provided approximately 8 hours and dinner approximately 12 hours postdose.

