9.4.2 Other Analyses (QTc and PK analyses)

Reference #	Endpoint	Statistical Analysis Methods
Primary		
1	$\Delta\Delta QTcF$ (evobrutinib)	A mixed-effects model with repeated measures will be used to analyze the relationship between evobrutinib concentrations and $\Delta\Delta QTcF$. Based on this model, the predicted $\Delta\Delta QTcF$ at clinically relevant concentrations will be calculated, with two-sided 90% confidence intervals. Model selection, including consideration of linear and nonlinear function to describe the C-QTc relationship, will be based on graphical exploration, along with standard goodness-of-fit plots. Additionally, the effects of evobrutinib on $\Delta\Delta QTcF$ will be descriptively summarized at each postdose timepoint (by timepoint analysis). Number and frequency of QTcF values within specified ranges will be summarized. Further details will be described in the IAP.
Secondary		
2	$\Delta\Delta QTcF$ (moxifloxacin)	Assay sensitivity will be demonstrated by showing that the lower bound of the 90% CI of the predicted $\Delta\Delta QTcF$ (from C-QTc model) for moxifloxacin at the observed geometric mean C_{max} at 400 mg dose exceeds 5 ms. Further details will be described in the IAP.
4	$\Delta\Delta HR$, $\Delta\Delta PR$, $\Delta\Delta RR$, $\Delta\Delta QRS$, T-wave morphology and U-wave	The effects of evobrutinib on these endpoints will be evaluated at each postdose timepoint (by timepoint analysis). Further details will be described in the IAP.
5	PK parameters (in Section 8.4)	Summary statistics of PK parameters will be provided. All PK analyses will be performed on the PKAS.

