16.3.3.1 Evaluation of Assumptions

Assessment of Drug Effect on HR

The potential of evobrutinib and MSC2729909A to increase or decrease heart rate by more than 10 bpm will be assessed graphically by plotting the mean observed Δ HR with 90% confidence interval versus timepoint for each treatment group and visually inspecting the trend of consistence with time and treatment group and, if applicable, based on model predicted Δ HR with 90% confidence versus corresponding evobrutinib and/or MSC2729909A plasma concentrations (see Section 16.3.4.2). Treatment groups with a small number of participants may be grouped together for this purpose. The Δ HR-concentration relationship may be further evaluated by scatter plots of individual time-matched Δ HR vs concentration pairs.

Hysteresis

To assess visually whether there is a time lag (a hysteresis effect) between evobrutinib plasma concentration and Δ QTc interval, mean concentration and mean Δ QTc will be plotted versus timepoint for each treatment group in a single plot and visually inspected for differences between t_{max} for concentration and t_{max} for Δ QTc. In addition, individual and mean plots showing Δ QTc and concentration connected in the order of ECG measurements/PK sampling will be shown for each study participant and evobrutinib treatment group, respectively. If the relationship between Δ QTc and evobrutinib plasma concentration appears independent of time, this suggests no hysteresis. If the exploration shows that the value of Δ QTc for a given value of concentration differs as time evolves, and the values of Δ QTc observed before t_{max} consistently differ from the values observed at a similar concentration at a timepoint after t_{max} , this suggests presence of hysteresis [1,3].

CCI

Assessment of Linearity

[figure not shown]
The relationship between observed ΔQTc and evobrutinib and MSC2729909A plasma concentrations will be visualized by decile plots showing mean observed ΔQTc with 90% confidence intervals placed at the midpoint of each concentration decile, as well as scatter plots of ΔQTc versus concentration for all timepoints from all treatment groups. Locally estimated scatterplot smoothing (LOESS) curve and linear regression lines will be included in the scatter plots.

CCI

[figure not shown]
[figure not shown]
[figure not shown]
[figure not shown]
[figure not shown]

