16.3.4.3 By Timepoint and Categorical Analysis

The Safety analysis set will be used for the analysis.

Triplet 10 s ECGs from continuous Holter recordings for central evaluation will also be extracted and evaluated statistically similar to standard safety ECG described in section 15.5.1. For the evaluation of continuous variables, the mean of each assessment at each time point with triplicates will be used in summary tables and for the evaluation of qualitative variables, the worst assessment will be used in summary tables, if not stated otherwise. Change from baseline will also be calculated and summarized.

This Holter ECG assessment include the parameters QT, QTcB, PR, QRS, RR, HR, and cardiologist assessment including T-wave morphology, and U-wave.

QTcI will be derived by log-linear regression. Individual correction factors (m_i) for log-transformed QT vs. log-transformed RR data for each subject at predose (-1 h, -30 min, -10 min) and from the placebo period will be fitted. QTcI will then be calculated as shown in [Equation 2](#)

$\Delta\Delta QTcF$, $\Delta\Delta QTcI$, $\Delta\Delta HR$, $\Delta\Delta PR$, $\Delta\Delta RR$, $\Delta\Delta QRS$, will be calculated as the difference between the change from baseline of active treatment (evobrutinib or moxifloxacin) and the time-matched change from baseline of placebo.

For $\Delta\Delta QTcF$, the postdose timepoint with the maximum mean for each active study intervention will be selected and tabulated together with the mean value and its 2-sided 90% confidence intervals (CI).

QT values will be categorized for each time point using the following groups

- ≤ 500 ms
- > 500 ms

Observed QTcF values will be categorized according to their absolute values into the categories

- ≤ 450 ms
- > 450 and ≤ 480 ms,
- > 480 and ≤ 500 ms, and
- > 500 ms,

and categorized according to their absolute change from baseline into the categories

- ≤ 30 ms,
- > 30 and ≤ 60 ms, and
- > 60 ms.

The number and percentage of subjects by these categories at each postdose assessment will be tabulated by study intervention.

A categorical analysis for outliers will be performed in order to identify the frequency of postdose categorical outliers for ECG parameters by study intervention:

The categorical outliers for HR parameters will be categorized as:

- HR changes reflecting at least a 25% decrease from baseline to a $HR < 50$ beats per minute (bpm) (Bradycardic event)

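### The concentration plots in SAP 16.3.4.2 use change from baseline without placebo subtraction, so a time effect shared by all arms can look like a concentration effect, above all for uncorrected QT

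*SAP*

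**What the plan says.** Objective 4 (Protocol section 3, SAP section 5) covers the effect of evobrutinib on QT, QTcB, QTcI, PR, QRS, RR and HR, plus T- and U-wave findings.

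- **SAP 16.3.4.2.** The response is "baseline-corrected measurements of uncorrected QT intervals, PR and QRS intervals, and HR". Its relation to concentration is to be "visually assessed by plots of the ECG measurements versus time-matched evobrutinib and MSC2729909A plasma concentrations with trend lines". That sentence names neither a time term nor placebo subtraction. Redacted text follows it.
- **SAP 16.3.4.3.** For QTcF, QTcI, HR, PR, RR and QRS a placebo-corrected value "will be calculated as the difference between the change from baseline of active treatment (evobrutinib or moxifloxacin) and the time-matched change from baseline of placebo". Uncorrected QT and QTcB are not in that list. They appear only in the Holter summaries of values and changes from baseline, with a 500 ms category for QT.
- **Protocol 9.4.2.** For objective 4 it lists placebo-corrected HR, PR, RR and QRS by timepoint, again without QT or QTcB.
- **SAP 16.3.2.** Mean absolute and baseline-corrected ECG measurements are plotted against nominal time for each treatment group, placebo included.
- **SAP 16.3.3.1.** The 10 bpm HR check starts from mean change in HR with a 90% interval, "versus timepoint for each treatment group and visually inspecting the trend of consistence with time and treatment group". If applicable it adds a model-predicted change "with 90% confidence versus corresponding evobrutinib and/or MSC2729909A plasma concentrations (see Section 16.3.4.2").
- **Protocol 5.3.1.** Participants fast until 4 h after dosing, when lunch is served. A snack follows at about 8 h and dinner at about 12 h.

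**The concern.** Concentration and time after dose are tightly linked in this design. All the high concentrations occur in the first hours, under fasting. Every ECG from 6 h onward (6, 8, 12, 16 and 24 h) follows a meal and falls at low concentration. If HR rises after lunch in all four periods, placebo included, the rise sits at the low end of the concentration axis. The trend line then shows HR falling with concentration. Because uncorrected QT shortens as HR rises, the line also shows QT lengthening with concentration, although the drug has done nothing.

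In a thorough QT study, an apparent rise of several milliseconds in QT with concentration invites misreading. For HR the artefact has the opposite sign and could mask part of a true increase.

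**Working it through.** The plan gives no figure on this point, so there is nothing to reproduce. The check asks how far a plain trend line tilts when the true drug effect is zero.

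**Inputs from the documents**
- Postdose ECG and PK times: 0.25, 0.5, 1, 1.5, 2, 2.5, 3, 4, 6, 8, 12, 16 and 24 h (Protocol 1.3).
- Fasted tmax 0.5 to 1.5 h, half-life about 2 h, dose-proportional PK (Protocol 2.2), so the 225 mg profile is 5 times the 45 mg profile.
- Lunch at 4 h (Protocol 5.3.1).

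**Assumptions, not in the documents**
- One-compartment oral profile with absorption rate 1.5 or 3.5 per hour, giving tmax 1.27 or 0.73 h.
- Shared HR rise of A = 4, 8 or 12 bpm at 6 h. The profile relative to A is 0 up to 4 h, 1.0 at 6 h, 0.6 at 8 h, 0.7 at 12 h, -0.2 at 16 h and 0 at 24 h.
- Baseline HR 60 bpm, and QT = 400 × (60/HR)^(1/3) ms, so QTcF stays constant at 400 ms.

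**Step 1: where the meal falls on the concentration axis.** As a fraction of Cmax, concentration at 4, 6 and 8 h is 0.50, 0.25 and 0.13 for tmax 1.27 h, and 0.36, 0.18 and 0.09 for tmax 0.73 h.

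**Step 2: slope for HR.** Take the 45 mg Cmax as the unit of concentration and use the 26 points from the two doses. The slope is Sxy/Sxx. For A = 4 and tmax 1.27 h it is -16.82/71.06 = -0.237 bpm per unit. The 225 mg Cmax is 5 units, so the false change there is 5 × (-0.237) = -1.18 bpm. For tmax 0.73 h it is 5 × (-17.17/64.45) = -1.33 bpm.

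**Step 3: the same for QT.** With A = 4, QT at 6 h is 400 × (60/64)^(1/3) - 400 = -8.5 ms. The fitted line gives +2.5 ms (tmax 1.27 h) or +2.9 ms (tmax 0.73 h) at the 225 mg Cmax.

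**Step 4: all settings.** Each range covers both tmax values, and fits with and without placebo records added at concentration zero.

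| Assumed HR rise at 6 h | False HR change at 225 mg Cmax | False uncorrected-QT change at 225 mg Cmax |
|---|---|---|
| 4 bpm | -0.9 to -1.3 bpm | +2.0 to +2.9 ms |
| 8 bpm | -1.9 to -2.7 bpm | +3.8 to +5.5 ms |
| 12 bpm | -2.8 to -4.0 bpm | +5.5 to +7.9 ms |

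Adding the placebo records removes only about a fifth of the artefact (for A = 4 and tmax 1.27 h, HR goes from -1.18 to -0.93 bpm).

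**Step 5: other meal shapes.** A rise peaking at 5 or 10 bpm was tried as lunch only, as lunch already affecting the 4 h ECG, and as persisting through snack and dinner. The false HR change then ran from -0.6 to -5.0 bpm. Every value is below 10 bpm.

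**Step 6: the remedy.** With time-matched placebo subtraction, or with time and treatment terms in the model, the false change is 0.0 in every setting checked.

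PR, QRS and the metabolite were not quantified.

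**The case against.** The strongest reply is that the plots are a supplement and the plan already holds what is needed to see through them. Most of this stands.

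- **Redaction.** A reader might infer that 16.3.4.2 contains no time-adjusted analysis at all. The documents do not support that. Text after the sentence is redacted, and 16.3.3.1 points to this section for a model-predicted change in HR. Whether that model has a time term cannot be read. The point is limited to the visible trend-line assessment.
- **HR, PR and QRS.** Protocol 9.4.2 makes the by-timepoint analysis the method for these, and SAP 16.3.4.3 derives the placebo-corrected values. A shared lunch response cancels there.
- **Uncorrected QT.** A reader might infer that nothing planned would contradict a false QT trend. That goes too far: 16.3.2 shows change by nominal time for each arm, so a meal response would be visible in the placebo curve. It remains true that no readable analysis subtracts placebo from QT or QTcB.
- **The 10 bpm rule.** A reader might infer that the artefact would upset the choice of QT correction or model. The first check in 16.3.3.1 is by time and treatment group, only the conditional step uses concentration, and the HR artefact stays below 10 bpm throughout.
- **Error rates.** A reader might want a false-positive rate. The readable text plans visual assessment with no slope test or decision rule, so such a rate would describe a test that is not planned.

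What the reply does not remove is that the trend lines themselves are drawn on a scale that leaves in any shared time effect.

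**Conclusion.** The point holds as a limited one. The trend lines described in the visible text of SAP 16.3.4.2 can show a concentration effect that is only a shared time effect. The size, about +2 to +8 ms for uncorrected QT and about -1 to -4 bpm for HR at the 225 mg Cmax, rests on an assumed shared HR rise of 4 to 12 bpm and its assumed time shape. With no shared rise there is no artefact. The direction follows from the early peak, short half-life and 4 h lunch.

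The case is strongest for uncorrected QT. QT and QTcB are objective 4 endpoints but are absent from the placebo-corrected list in 16.3.4.3. The primary C-QTc analysis is not affected: SAP 16.3.3.3 treats nominal time as part of the C-QTc models, and 16.3.3.5 subtracts the placebo prediction. This is a worthwhile, low-cost improvement to a secondary display and does not threaten the study's main conclusion.

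**What to change.** 1. In SAP 16.3.4.2, plot the time-matched placebo-corrected change of QT, PR, QRS and HR (active minus the same participant's placebo change at the same nominal time) against concentration, and draw the trend lines on those values.
2. In SAP 16.3.4.3, add placebo-corrected QT and QTcB to the list of derived values.
3. If the redacted part of 16.3.4.2 holds a concentration model, confirm that it includes nominal time.

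The cost is SAP wording and a change of plotted variable. The HR, PR and QRS values are already derived, and QT and QTcB need the same subtraction. There are two small downsides: each point carries the placebo measurement's noise as well as its own, and records without a matching placebo value are lost from the plots.

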16.3.4.3 By Timepoint and Categorical Analysis

The Safety analysis set will be used for the analysis.

Triplet 10 s ECGs from continuous Holter recordings for central evaluation will also be extracted and evaluated statistically similar to standard safety ECG described in section 15.5.1. For the evaluation of continuous variables, the mean of each assessment at each time point with triplicates will be used in summary tables and for the evaluation of qualitative variables, the worst assessment will be used in summary tables, if not stated otherwise. Change from baseline will also be calculated and summarized.

This Holter ECG assessment include the parameters QT, QTcB, PR, QRS, RR, HR, and cardiologist assessment including T-wave morphology, and U-wave.

QTcI will be derived by log-linear regression. Individual correction factors (m_i) for log-transformed QT vs. log-transformed RR data for each subject at predose (-1 h, -30 min, -10 min) and from the placebo period will be fitted. QTcI will then be calculated as shown in [Equation 2](#)

$\Delta\Delta QTcF$, $\Delta\Delta QTcI$, $\Delta\Delta HR$, $\Delta\Delta PR$, $\Delta\Delta RR$, $\Delta\Delta QRS$, will be calculated as the difference between the change from baseline of active treatment (evobrutinib or moxifloxacin) and the time-matched change from baseline of placebo.

For $\Delta\Delta QTcF$, the postdose timepoint with the maximum mean for each active study intervention will be selected and tabulated together with the mean value and its 2-sided 90% confidence intervals (CI).

QT values will be categorized for each time point using the following groups

- ≤ 500 ms
- > 500 ms

Observed QTcF values will be categorized according to their absolute values into the categories

- ≤ 450 ms
- > 450 and ≤ 480 ms,
- > 480 and ≤ 500 ms, and
- > 500 ms,

and categorized according to their absolute change from baseline into the categories

- ≤ 30 ms,
- > 30 and ≤ 60 ms, and
- > 60 ms.

The number and percentage of subjects by these categories at each postdose assessment will be tabulated by study intervention.

A categorical analysis for outliers will be performed in order to identify the frequency of postdose categorical outliers for ECG parameters by study intervention:

The categorical outliers for HR parameters will be categorized as:

- HR changes reflecting at least a 25% decrease from baseline to a $HR < 50$ beats per minute (bpm) (Bradycardic event)
- HR changes with a 25% increase from baseline reflecting a $HR > 100$ bpm (Tachycardic event)

The categorical outliers for PR and QRS parameters will be categorized as:

- PR change from baseline: at least a 25% increase when $PR > 200$ msec
- QRS change from baseline: at least a 25% increase when $QRS > 100$ msec

The number and percentage of subjects by these categories at each post-dose assessment will be tabulated by treatment group.

The results for T-wave morphology (abnormal+finding) and U-wave (abnormal) will be summarized in frequency tables with counts and percentages for number of subjects.

17

References

18 Appendices

Not applicable.

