Triplicate ECGs from Holter recordings			X	X		X	X		X	X		X	X		On each dosing day 12-lead ECGs extracted in triplicates from Holter recordings at 3 timepoints before dosing (-1 h, -30 min, and -10 min), and at 15 and 30 min and 1, 1.5, 2, 2.5 3, 4, 6, 8, 12, 16 h and at 24 h postdose.
Clinical laboratory safety tests	X	X			X			X			X		X		Blood samples for the clinical laboratory safety assessments will be collected in a fasted condition.
PK sampling (evobrutinib, evobrutinib major metabolite, and moxifloxacin)			X	X		X	X		X	X		X	X		Plasma samples for PK analysis will be collected on the days of dosing (i.e., Days 1, 8, 15, and 22) at predose and 15 and 30 min, and 1, 1.5, 2, 2.5, 3, 4, 6, 8, 12, 16 and 24 h postdose. At visits where assessment time points coincide with each other, the following sequence of activities will be followed: PK sample to be collected shortly (within time windows specified) after ECG.
Study intervention administration			X			X			X			X			
Previous/concomitant medication monitoring	X	<=====>													Section 6.8.
AE monitoring	X	<=====>													Section 8.3.

CRU=clinical research unit; ECG=electrocardiogram; eGFR=estimated glomerular filtration rate; FSH=follicle stimulating hormone; PK=pharmacokinetics; SARS-CoV-2=severe acute respiratory syndrome coronavirus 2; TSH=thyroid stimulating hormone.

2

[figure not shown]
Introduction

Evobrutinib is an oral, selective, irreversible inhibitor of BTK that is in clinical development for the treatment of autoimmune diseases, e.g. RMS. Detailed information on the chemistry, pharmacology, efficacy, and safety of evobrutinib is in the current IB.

This study is being conducted to assess potential effects of evobrutinib on cardiac repolarization (i.e., prolongation of QT interval).

CC1

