Within the ECG laboratory, the staff involved with ECG interval measurements and morphological analyses will be blinded with regard to treatment, date and time as well as time points of the ECG measurements. No more than 2 blinded readers will evaluate all ECGs of the study. The interval measurements for a given participant will be performed in random and blinded sequence by a single reader. For quality assurance and control of the measurements, all ECGs of an individual participant will be subsequently reviewed by the ECG technician supervisor or his/her designee to assess the overall variance of the measured intervals and to detect accidental switching of leads and/or false participant assignments of the ECGs.

In addition to the measurements of the intervals, one randomly selected ECG at each time point will be evaluated by a board-certified cardiologist. This evaluation will include an overall assessment as well as specific findings regarding rhythm, conduction, ST-T segment and T/U-wave, morphology, and myocardial infarction. Standard CDISC terms will be used for this interpretation of the ECG. The cardiologist will review the ECGs one by one and in random order. Thus, she/he is practically blinded to the sequence of the ECG within a participant. After

evaluation of the ECGs, the results will be submitted to the data management company using a predefined data transfer method and specification. The transfer will include for any ECG recording classified as “abnormal” the description of the abnormality in addition to the clinical relevance (yes/no).

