| To assess the effect of evobrutinib on other ECG parameters | QT, QTcB, QTcl, PR, QRS, RR, HR, cardiologist assessment including T-wave morphology, and U-wave. | 4 |
| To determine the PK of evobrutinib and its major metabolite at 45 mg and 225 mg oral dose (solution) under fasting conditions and moxifloxacin at 400 mg oral dose | AUC ₀₋₂₄ , AUC _{0-∞} , C _{max} , and t _{max} for evobrutinib and major metabolite AUC ₀₋₂₄ , AUC _{0-∞} , C _{max} , and t _{max} for moxifloxacin | 5 |

6 Overview of Planned Analyses

The final, planned analyses identified in the CSP and in this IAP will be performed after the last participant has completed the last visit and after all data queries resolved as well as the database locked.

A data review meeting will be held prior to database lock for the final analysis. In addition, no database can be locked until this IAP has been approved.

7 Changes to the Planned Analyses in the Clinical Study Protocol

Not applicable.

8 Analysis Sets and Subgroups

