9.1 Definition of Baseline and Change from Baseline

If not otherwise specified, 'baseline' refers to the last scheduled measurement before administration of study intervention in each period.

However, if a participant is missing the baseline collection, the previous non-missing evaluation could become the baseline value (e.g. from Screening). If no baseline or previous to baseline evaluations exist, then the baseline value will be treated as missing.

For the ECG measurements, 'baseline' refers to the average of the derived ECG intervals from the three ECG timepoints prior to dosing on day 1 within each respective period.

Absolute changes from baseline are defined as

$$\text{absolute change} = \text{visit value} - \text{baseline value}$$

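### SAP 16.3.4.3 counts abnormal T-wave and U-wave findings without separating those already present predose from new ones

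*SAP*

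**What the plan says.** T-wave morphology and U-wave are named endpoints under the fourth objective, "To assess the effect of evobrutinib on other ECG parameters" (SAP section 5). Protocol 9.4.2 says the evobrutinib effect on them will be assessed time point by time point after dosing, and leaves the detail to the analysis plan.

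The detail in SAP 16.3.4.3 is one sentence: "The results for T-wave morphology (abnormal+finding) and U-wave (abnormal) will be summarized in frequency tables with counts and percentages for number of subjects". Three other provisions bear on it:

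- SAP 9.1 defines the ECG baseline as "the average of the derived ECG intervals from the three ECG timepoints prior to dosing on day 1" in each period.
- SAP 16.3.4.3 says of the Holter ECGs in general: "Change from baseline will also be calculated and summarized".
- SAP 16.3.4.3 also says that "for the evaluation of qualitative variables, the worst assessment will be used in summary tables, if not stated otherwise", while Protocol 8.4.3 says that "one randomly selected ECG at each time point will be evaluated by a board-certified cardiologist".

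The schedule of activities (Protocol 1.3) has three predose ECG times and 13 postdose ECG times in every period, so predose cardiologist readings are already planned.

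**The concern.** The objective asks what the drug does. A count of abnormal readings gives the same weight to a long-standing flat T wave as to one that appears after dosing.

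Pre-existing findings are possible in this population. Exclusion criterion 21 sets screening ECG limits for QTcF, PR and QRS only. T-wave and U-wave findings are left to the investigator's general judgement on eligibility.

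No other text supplies a baseline rule for these findings. An average of intervals cannot be formed for a qualitative reading, and the general change-from-baseline sentence does not say what change means for a category. SAP 15.5.1, on which the Holter evaluation is modelled, tabulates interpretation categories without a shift from predose.

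What is at stake is how readable a cardiac-safety table will be. A non-zero percentage under evobrutinib cannot be taken as drug-induced, and the within-period comparison that the design makes possible is not used for this endpoint.

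**Working it through.** The plan gives no expected rate for T-wave or U-wave findings, and the sample-size text is redacted, so there is no figure to reproduce. The rates and the number of participants below are assumptions, chosen to show how the planned table behaves.

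**1. What the planned percentages contain.** Let b be the share of participants with a stable finding present in every period, and let e0 and e1 be the probabilities of a new finding under placebo and evobrutinib among the others.

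- Planned percentage per treatment: b + (1 − b)·e
- Planned difference, evobrutinib minus placebo: (1 − b)·(e1 − e0)
- Treatment-emergent percentage over all participants: (1 − b)·e
- Treatment-emergent percentage over those free of the finding predose: e

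With e0 = 2% and e1 = 12%:

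| b | Planned: placebo | Planned: evobrutinib | Difference (points) | Emergent, all participants: placebo / evobrutinib |
|---|---|---|---|---|
| 2% | 4.0% | 13.8% | 9.8 | 2.0% / 11.8% |
| 5% | 6.9% | 16.4% | 9.5 | 1.9% / 11.4% |
| 10% | 11.8% | 20.8% | 9.0 | 1.8% / 10.8% |
| 20% | 21.6% | 29.6% | 8.0 | 1.6% / 9.6% |

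The background raises every column. The difference between treatments equals that of an emergent table over all participants. Relative to participants free of the finding predose (10 points at every b), it shrinks only by the factor 1 − b, that is 0.98 to 0.80.

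**2. What the counts leave open.** Take 40 participants and b = 10%, so 40 × 0.10 = 4 have a pre-existing finding. Two new cases at 225 mg and none on placebo give 6/40 against 4/40 as planned, and 2/36 against 0/36 as treatment-emergent. But 6/40 against 4/40 fits two different situations:

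- four participants abnormal in both periods and two only on evobrutinib;
- six abnormal only on evobrutinib and four others only on placebo.

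The planned table cannot tell these apart, and no paired comparison with placebo is specified. The list of placebo-corrected parameters in SAP 16.3.4.3 does not include morphology.

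**3. Where background does not cancel.** If two of the 40 have a finding that is already there predose in the 225 mg period, persists after dosing, and is absent from the placebo period, the planned table shows an excess of 2/40 = 5 points with no drug effect. Dropout has a similar effect: the safety set includes anyone given any dose (SAP 8.1) and missing data are not handled (SAP 9.4), so the columns need not contain the same people.

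**4. Check on the remedy.** Suppose a finding comes and goes, with a 20% chance at each independent reading.

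- Absent from all three predose readings: 0.8^3 = 0.512
- Present in at least one of 13 postdose readings: 1 − 0.8^13 = 0.945
- Counted as emergent: 0.512 × 0.945 = 0.48

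About 48% of such participants would be counted as emergent in any period, placebo included. An emergent count must therefore also be read against placebo.

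**The case against.** The strongest reply is that placebo already deals with background. SAP section 9 summarises data by study intervention and/or time point, the Holter ECGs follow SAP 15.5.1, which tabulates by study intervention and time point, and each participant is planned to receive all four treatments. A stable finding therefore appears in the placebo column too, and step 1 confirms that the contrast is preserved. This stands. A reader might infer that the tables show background prevalence instead of a drug effect, and the documents do not support that. A smaller reservation is that the T-wave and U-wave sentence does not itself mention study intervention or postdose time, so the placebo column rests on the general rules.

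Two other strong readings also fail:

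- Morphology is not the only ECG outcome without a baseline reference. The absolute QT and QTcF categories in the same section have none, although QTcF also has change-from-baseline categories.
- Equal percentages cannot hide new cases if the background is stable, because any new case raises the evobrutinib count. Hiding needs findings that differ between periods.

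It can also be said that all individual data are listed by participant and time, so a reader can check by hand whether a finding was there predose. That is true, but it leaves the sorting of new from old to each reader, without a stated rule.

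Finally, the worst-assessment rule changes no number: with one cardiologist-read ECG per time point, the worst reading is that reading. This is a wording point only.

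**Conclusion.** The point holds in a limited form. The plan has no rule that separates pre-existing from new T-wave or U-wave findings, so single-treatment percentages cannot be read as treatment-emergent. The counts also do not identify who changed, and findings present predose in only one period do not cancel. The comparison with placebo survives and, for stable background, loses little: a factor of 0.80 at worst for b up to 20%.

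The severity is low. The endpoint is secondary and descriptive, and the primary concentration-QTc analysis is not touched. The sizes shown rest on an assumed 40 participants, assumed background and new-onset rates, and, in steps 1 and 2, a background that is the same in every period.

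**What to change.** Add to SAP 16.3.4.3 a treatment-emergent T-wave or U-wave count: a finding present at any postdose time in a period and absent from all three predose readings of that period. Tabulate it by study intervention including placebo, overall and by time point. Use as denominator the participants free of that finding predose, and show pre-existing findings in a separate row. State that the count is to be read beside placebo.

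In the same edit, align the worst-assessment wording with the single cardiologist-read ECG per time point in Protocol 8.4.3.

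The cost is SAP wording and one derived flag, with no extra ECG or reader. There are two drawbacks. With 13 postdose readings against three predose, an intermittent finding can count as emergent under any treatment. And a pre-existing finding that worsens is seen only if its recorded category changes.
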